## 1.7 STATISTICAL ADAPTATIONS MADE IN THE STATISTICAL ANALYSIS PLAN FROM THE PROTOCOL BEFORE STUDY START

In this section, summarize major adaptations in statistical analysis features made in approved SAP versions, with emphasis on adaptations before study start (before the first patient was enrolled)

The table below gives the timing, rationale, and key details of major adaptations made in the SAP from the protocol.

The first patient is planned to be enrolled on 16-Nov-2016. There are no planned interim analysis.

**Table 1 - Adaptations to statistical analysis plan from protocol before study start**

Protocol Amendment Number	Date Approved	Rationale	Description of statistical changes
1	19-Aug-2016	To be detailed.	The definition of normalized TAV (Median number of analyzed frames in the population) was detailed.
		To correct the erroneous description about calculation of normalized TAV.	Normalized TAV will be calculated by Sanofi or delegate, not Central Reading.
		To be detailed	The definition of primary analysis population, modified Intent-to-treat population was added to have post-baseline during efficacy treatment period
		To be detailed	Congestive heart failure will be also adjudicated by Clinical Events Committee

## 2 STATISTICAL AND ANALYTICAL PROCEDURES

### 2.1 ANALYSIS ENDPOINTS

#### 2.1.1 Demographic and baseline characteristics

Unless otherwise specified, the baseline value is defined as the last available value before randomization.

All baseline safety and efficacy parameters (apart from those listed below) are presented along with the on-treatment summary statistics in the safety and efficacy sections ([Section 2.4.5](#) and [Section 2.4.4](#)).

#### *Demographic characteristics*

Demographic variables are:

- Age in years (quantitative and qualitative variable: <65, ≥65 to <75, and ≥75 years; and <65, ≥65 years);
- Gender (Male, Female);
- Race (Asian);
- Ethnicity (Not Hispanic or Latino).

#### *Medical or surgical history*

This information will be coded using the version of Medical Dictionary for Regulatory Activities (MedDRA) currently in effect at Sanofi or delegate at the time of database lock.

Medical history of specific interest includes:

- CHD prior to the index ACS diagnosis;
  - Myocardial infarction
  - Unstable angina
  - Coronary revascularization procedure
  - Other clinically significant CHD
- Ischemic stroke
- Peripheral arterial disease
- Hypertension
- Diabetes
  - Type 1 diabetes

- Type 2 diabetes
- Chronic kidney disease (CKD)
- Impaired glucose tolerance
- Hypo HDL cholesterolemia (<40 mg/dL)
- Family history of premature coronary artery disease
- Family history of Type 2 diabetes mellitus

“Peripheral Arterial Disease” history is defined as follows, using combinations of the corresponding pre-listed medical history items of the e-CRF page “Cardiovascular history and cardiovascular risk factors”:

- Intermittent claudication (linked to PAD) TOGETHER WITH ankle-brachial index  $\leq 0.90$   
Or
- Intermittent claudication (linked to PAD) TOGETHER WITH peripheral revascularization procedure (angioplasty, stenting) for PAD or peripheral revascularization surgery (arterial bypass) for PAD  
Or
- Critical limb ischemia TOGETHER WITH peripheral revascularization procedure (angioplasty, stenting) for PAD or thrombolysis for PAD or peripheral revascularization surgery (arterial bypass) for PAD.

The status of hypertension at baseline will be selected using SMQ “hypertension” (narrow), based on terms reported as “ongoing” in Medical history by the investigator.

Efficacy and safety analysis performed according to “**diabetic status at baseline**” reported in the Medical history by the investigator will be done using a company MedDRA query (CMQ), based on the following PTs reported in e-CRF Medical History: “diabetes mellitus”, “diabetes mellitus inadequate control”, “fulminant type 1 diabetes mellitus”, “insulin resistant diabetes”, “insulin-requiring type 2 diabetes mellitus”, “type 1 diabetes mellitus”, “type 2 diabetes mellitus”, “diabetes mellitus malnutrition-related”, and “diabetes mellitus management”.

Diabetic status at baseline (Yes, No) will be also summarized. Besides, for diabetic patients at baseline, the following items will be summarized.

- Insulin use (Yes, No);
- Time from diagnosis of diabetes (quantitative [years] and qualitative variable:  $<\text{Median}$ ,  $\geq \text{Median}$  years).

Medical or surgical history includes:

- Medical history of allergies;
- Smoking habits (Never, Former, Current);

- Alcohol habits (Never, Occasional, At least monthly, At least weekly, At least daily).

### ***Disease characteristics at baseline***

Specific disease history includes:

- The index ACS subtype (acute ST-segment elevation myocardial infarction [STEMI], acute non ST-segment elevation myocardial infarction [NSTEMI], unstable angina [UA])
- Time from the index ACS diagnosis to randomization (in weeks), quantitatively and in category <2, ≥2 to <4, ≥4 weeks
- Revascularization procedure associated with the index ACS event (PCI or CABG)
- Time from the revascularization procedure to randomization (in weeks)
- Types of stents placed at the PCI (bare metal stent [BMS], drug eluting stent [DES] or both).
- Location of ACS culprit vessels
- Location of analyzed IVUS imaging vessels (RCA, LAD, LCX, Other)
- New cardiovascular events occurring after the index ACS diagnosis and before randomization, selected using e-CRF specific tick box on the adverse event page.
- Type of hypercholesterolemia:
  - Heterozygous familial hypercholesterolemia (heFH);
  - Non-familial hypercholesterolemia (non-FH);
  - Unknown;
- For heFH patients:
  - Time from diagnosis of heFH (years);
  - Diagnosis made by genotyping (Yes, No);
- For non-FH patients:
  - Time from diagnosis of hypercholesterolemia (years);
  - Fredrickson classification of hyperlipoproteinemia (IIa, IIb, IV);
- The background lipid modifying therapy (LMT) regimen at ACS diagnosis, as reported in the “Previous Lipid Modifying Therapy” e-CRF page, will be summarized using the following categories:
  - Any LMT
  - Any statin by daily dose
    - Atorvastatin, rosuvastatin, pravastatin, simvastatin, fluvastatin, pitavastatin
  - LMT other than statin
    - Ezetimibe

Fibrate

- Fenofibrate
- Bezafibrate
- Other
- Other

- The background lipid modifying therapy regimen at randomization, as reported in the “Previous Lipid Modifying Therapy” e-CRF page, will be summarized as those at ACS diagnosis.

***Other baseline characteristics***

Other baseline characteristics include weight in kilograms (quantitative variable and qualitative variable: <Median,  $\geq$ Median), body mass index (BMI) in kg/m^2 (quantitative and qualitative variable: <25,  $\geq$ 25), and randomization strata (as described in [Section 1.1](#)) as per registration center.

Lipid parameters and glycated hemoglobin A1c (HbA1c) (quantitative and qualitative variable: <5.7 %,  $\geq$ 5.7 to <6.5%,  $\geq$ 6.5%), hs-CRP (quantitative [mg/L, mg/dL] and qualitative variable: <2,  $\geq$ 2 mg/L [ie, <0.2 mg/dL,  $\geq$ 0.2 mg/dL]), and eGFR (quantitative and qualitative variable: <15,  $\geq$ 15 to <30,  $\geq$ 30 to <60,  $\geq$ 60 to <90,  $\geq$ 90 mL/min/1.73m^2, category <30,  $\geq$ 30, <60,  $\geq$ 60 mL/min/1.73m^2 will be also displayed) at baseline will be also summarized by treatment group. Lipid parameters are total cholesterol (TC), calculated LDL-C, non HDL-C, high-density lipoprotein cholesterol (HDL-C), fasting TGs, Apo A-1, Apo B, Lp (a), Apo B/Apo A-1 ratio, Fasting TGs/HDL-C ratio, and calculated LDL-C/HDL-C ratio. Lipids parameters will be summarized using standard international unit and conventional unit. Baseline values of lipid parameters are defined as the last available value from central laboratory assessed up to the date and time of randomization. eGFR will be calculated using the equation defined in [Section 2.5.1](#).

For lipid parameters, both quantitative and qualitative variables will be considered, with the following categories:

- Calculated LDL-C: <70,  $\geq$ 70 to <80,  $\geq$ 80 to <100,  $\geq$ 100 to <130,  $\geq$ 130 to <160,  $\geq$ 160 to <190,  $\geq$ 190 mg/dL (ie, <1.81,  $\geq$ 1.81 to <2.07,  $\geq$ 2.07 to <2.59,  $\geq$ 2.59 to <3.37,  $\geq$ 3.37 to <4.14,  $\geq$ 4.14 to <4.91,  $\geq$ 4.91 mmol/L), category <100,  $\geq$ 100 mg/dL (ie, <2.59,  $\geq$ 2.59 mmol/L) and <80,  $\geq$ 160 mg/dL (<2.07,  $\geq$ 4.14 mmol/L) will be also displayed,
- HDL-C: <40,  $\geq$ 40 mg/dL (ie, <1.04,  $\geq$ 1.04 mmol/L),
- Non-HDL-C: <100,  $\geq$ 100 to <110,  $\geq$ 110 to <130,  $\geq$ 130 to <160,  $\geq$ 160 to <190,  $\geq$ 190 to <220,  $\geq$ 220 mg/dL (ie, <2.59,  $\geq$ 2.59 to 2.84,  $\geq$ 2.84 to <3.37,  $\geq$ 3.37 to <4.14,  $\geq$ 4.14 to <4.91,  $\geq$ 4.91 to 5.69,  $\geq$ 5.69 mmol/L), category <110,  $\geq$ 130 mg/dL, (ie, <2.84,  $\geq$ 3.37 mmol/L) will be also displayed
- Fasting TGs: <150,  $\geq$ 150 to <200,  $\geq$ 200 mg/dL (ie, <1.7,  $\geq$ 1.7 to <2.3,  $\geq$ 2.3 mmol/L), category  $\geq$ 150 mg/dL (ie,  $\geq$ 1.7 mmol/L [mixed dyslipidemia]) will be also displayed,

- Lp (a): <30,  $\geq 30$  to <50,  $\geq 50$  mg/dL (ie, <0.3,  $\geq 0.3$  to <0.5,  $\geq 0.5$  g/L), category  $\geq 30$  , <50 mg/dL, (ie,  $\geq 0.3$ , <0.5 g/L) will be also displayed
- Apo B: <75,  $\geq 75$  to <90,  $\geq 90$  mg/dL (ie, <0.75,  $\geq 0.75$  to <0.9,  $\geq 0.9$  g/L)

Lipid parameters at patient selection and HbA1c at ACS diagnosis (quantitative and qualitative variable) will be also analyzed as those at baseline. Lipid parameters at patient selection are to be reported in the case report “Lipid Parameters at Patient Selection” form page:

Note: non-HDL-C will be calculated by subtracting HDL-C from the TC.

Ratio Apo B/Apo A-1 will be calculated by Apo B divided by Apo A-1. If LDL-C was directly measured, LDL-C will be calculated using the Friedwald formula. If TG values exceed 400 mg/dL (4.52 mmol/L), then calculated LDL-C will be missing.

IVUS parameters (quantitative variables) and analyzed vessel length at baseline will be summarized. IVUS parameters are normalized TAV, PAV, external elastic membrane (EEM) volume, lumen volume, and TAV. For normalized TAV and PAV, quantitative variables will be also considered, with the following category (<Median,  $\geq$ Median).

Any technical details related to computation, dates, and imputation for missing dates are described in [Section 2.5](#).

## 2.1.2 Prior or concomitant medications

All LMTs taken within 1 month before Visit 1 and until the end of the study are to be reported in the case report form pages. Other concomitant medications taken since informed consent until the end of study are to be reported in the case report form page:

- Previous Lipid Modifying Therapy
  - Previous lipid modifying therapies are to be reported.
- Concomitant Non-Investigational Medicinal Product
  - Concomitant Non-Investigational Medical Product (NIMP) defined in protocol are to be reported.
- Concomitant Other Medication
  - Concomitant medications except NIMPs are to be reported.

All medications will be coded using the World Health Organization-Drug Dictionary (WHO-DD) using the version currently in effect at Sanofi or delegate at the time of database lock.

- Prior medications are those the patient used within 1 month prior to randomization. Prior medications can be discontinued before randomization or can be ongoing during treatment phase;
- Concomitant medications are any treatments received by the patient concomitantly to the treatment, from randomization to the last study treatment administration + 21 days, or end of study, whichever comes first. A given medication can be classified both as a prior

medication and as a concomitant medication. Concomitant medications do not include medications started during the post-treatment period (as defined in the observation period in [Section 2.1.4](#)).

- Post-treatment medications are those the patient took in the period starting the day after the end of treatment-emergent adverse event period (as defined in the observation period in [Section 2.1.4](#)) up to the end of the study.

For patients randomized but not treated, medications will be categorized as prior medications or post-treatment medications according to the date of intake in relation to the date of randomization.

The following medications of specific interest including NIMP defined in protocol will be selected using specific coding list specified in [Table 5](#), unless otherwise specified:

- Anti-platelets
  - Oral adenosine diphosphate (ADP) receptor antagonists (except aspirin)
    - Clopidogrel
    - Ticagrelor
    - Prasugrel
    - Ticlopidine
- Anticoagulants
  - Injectable anticoagulants (unfractionated heparin [UFH], low molecular weight heparin [LMWH], bivalirudin, selective factor Xa inhibitor)
  - Specific oral anticoagulants
    - Vitamin K antagonist (VKA)
    - Non-vitamin K antagonist oral anticoagulants (NOAC)
- Thrombolytic
- Anti-diabetic drugs
  - Oral hypoglycemic drugs
    - Biguanides/metformin
    - Sulfonylurea
    - Glinide
    - Thiazolidine dione (TZD)
    - Alpha-glucosidase inhibitors ( $\alpha$ -GI)
    - DPP4 inhibitor
    - SGLT2 inhibitor
  - Injectable hypoglycemic drugs
    - Glucagon-like peptide-1 receptor agonists (GLP-1 RA)
    - Insulin
- Angiotensin-converting-enzyme (ACE)-inhibitor or angiotensin receptor blocker
- Beta blocker

- Calcium channel blocker
- Diuretics
- Nitrates
- Non-steroidal anti-inflammatory drugs (NSAIDs) (excluding aspirin)
- Cholesterol absorption inhibitor
  - Ezetimibe
- Fibrate
  - Fenofibrate
  - Bezafibrate

Any technical details related to computation, dates, imputation for missing dates are described in [Section 2.5](#).

### 2.1.3 Efficacy endpoints

The EEM volume, lumen volume, TAV, normalized TAV, and PAV will be calculated by the Sponsor or delegate. These IVUS parameters will be calculated using the following equations defined using  $EEM_{CSA}$  and  $Lumen_{CSA}$  taken at pre-determined interval between each image ( $\delta=0.5$  mm):

$$TAV \text{ (mm}^3\text{)} = \sum (EEM_{CSA} - Lumen_{CSA})\delta,$$

$$\text{normalized TAV (mm}^3\text{)} = TAV \times \frac{C}{n},$$

where  $\Sigma$  is the summation over all the analyzed frames,  $n$  is the number of analyzed frames per patient,  $C$  is the median of the number of analyzed frames in patients with available baseline TAV within randomized population.  $EEM_{CSA}$  is the cross-sectional area inside the EEM border, the  $Lumen_{CSA}$  is the cross-sectional area inside the lumen border, and both parameters are measured by the central reading laboratory. Besides,

$$PAV \text{ (\%)} = \left( \frac{\sum (EEM_{CSA} - Lumen_{CSA})}{\sum EEM_{CSA}} \right) \times 100,$$

$$EEM \text{ volume (mm}^3\text{)} = \sum (EEM_{CSA})\delta,$$

$$\text{Lumen volume (mm}^3\text{)} = \sum (Lumen_{CSA})\delta,$$

where  $\Sigma$  is the summation over all the analyzed frames.

The detailed procedures of IVUS image analysis and calculation of the parameters will be specified in the procedure manual of IVUS image analysis.

For post-baseline IVUS parameters, the value used for the analyses at Week 36 is the value assessed after the  $\geq 24$  weeks of treatment and within the Week 36 analysis window defined in [Section 2.5.4.1, Table 3](#).

Efficacy parameters include lipid parameters (i.e. TC, calculated LDL-C, HDL-C, fasting TGs, non-HDL-C, Apo B, Apo A-1, Apo B/Apo A-1 ratio, Lp[a], fasting TGs/HDL-C ratio, and calculated LDL-C/HDL-C ratio). All these parameters except for fasting TGs/HDL-C ratio, and calculated LDL-C/HDL-C ratio are measured or calculated by the central laboratory, for both scheduled and unscheduled time points. The LDL-C will be calculated using the Friedewald formula. If TGs values exceed 400 mg/dL (4.52 mmol/L), the calculated LDL-C levels will not be used for any analysis. Non-HDL-C will be calculated by subtracting HDL-C from the TC. Apo B/Apo A-1 ratio will be calculated. Fasting TGs/HDL-C ratio, and calculated LDL-C/HDL-C ratio will be calculated by Sanofi or delegate.

Unless otherwise specified, all lipid values from central laboratory (scheduled or unscheduled, fasting or not fasting) will be used to provide a value for the secondary efficacy endpoints. All measurements, scheduled or unscheduled, fasting or not fasting (except for TGs), will be assigned to analysis windows as defined in [Section 2.5.4, Table 4](#) in order to provide an assessment for Week 4 to Week 36 time points. For TGs, only fasting measurements will be used. Measurements with missing fasting status will be excluded from the analyses.

For all time points, the value of post-baseline lipid parameters used for the analyses at a given time point (eg, at Week 36) is the value assessed and within the corresponding analysis window. The baseline value is the last available value from central laboratory assessed up to the date and time of randomization.

### **2.1.3.1 Primary efficacy endpoint**

The primary efficacy endpoint is the percent change in normalized TAV from baseline to Week 36, which is defined as:  $100 \times (\text{normalized TAV value at Week 36} - \text{normalized TAV value at baseline}) / \text{normalized TAV value at baseline}$  and calculated by Sponsor or delegate.

The baseline normalized TAV value is the one assessed before the randomization.

The normalized TAV at Week 36 will be the one assessed after the  $\geq 24$  weeks of treatment and within the Week 36 analysis window, defined in [Section 2.1.3](#).

### **2.1.3.2 Secondary efficacy endpoint(s)**

#### **2.1.3.2.1 Key secondary efficacy endpoint**

- Absolute change in PAV from baseline to Week 36.

#### 2.1.3.2.2 *Other secondary efficacy endpoints*

- Absolute change in normalized TAV from baseline to Week 36.
- Absolute and percent changes in EEM volume from baseline to Week 36.
- Absolute and percent changes in lumen volume from baseline to Week 36.
- Absolute and percent changes in TAV from baseline to Week 36.
- Absolute and percent changes in calculated LDL-C from baseline to Week 12, and Week 36.
- Absolute and percent changes in Apo B from baseline to Week 36.
- Absolute and percent changes in non-HDL-C from baseline to Week 36.
- Absolute and percent changes in TC from baseline to Week 36.
- Absolute and percent changes in Lp(a) from baseline to Week 36.
- Absolute and percent changes in HDL-C from baseline to Week 36.
- Absolute and percent changes in fasting TGs from baseline to Week 36.
- Absolute and percent change in Apo A-1 from baseline to Week 36.
- Absolute change in Apo B/Apo A-1 ratio from baseline to Week 36.
- Absolute change in fasting TGs/HDL-C ratio from baseline to Week 36.
- Absolute change in calculated LDL-C/HDL-C ratio from baseline to Week 36.
- The proportion of patients with calculated LDL-C <70 mg/dL (1.81 mmol/L) at Week 36
- The proportion of patients with calculated LDL-C <50 mg/dL (3.37 mmol/L) at Week 36
- The proportion of patients achieving at least 50% reduction in calculated LDL-C at Week 36

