##### **2.1.5.3 Patients with LDL-C <25 mg/dL (0.65 mmol/L)**

The assessment will include:

- The proportion of patients with two consecutive results, spaced out by at least 21 days, of LDL-C <25 mg/dL (<0.65 mmol/L) (respectively LDL-C <15 mg/dL, ie, <0.39 mmol/L) during the treatment period
- The time to the first LDL-C <25 mg/dL (respectively LDL-C <15 mg/dL) for these patients.

Only calculated LDL-C will be used for this endpoint.

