### ***Subgroup analyses (Stratified analyses)***

To assess the homogeneity of the treatment effect across various subgroups, treatment group-by-subgroup factor interaction terms and a subgroup factor term will be added in the primary ANCOVA model. LS means difference versus SoC will be provided, as well as the corresponding SE and 95% CI, within each subgroup. The significance level of the treatment group-by-subgroup factor interaction term will be also provided for each factor for descriptive purpose. Forest plots will be provided.

Subgroups of interest are (providing sufficient number of patients per subgroups):

- Baseline normalized TAV(<Median,  $\geq$  Median) for this specific subgroup factor, the ANCOVA model will include this categorical baseline instead of continuous baseline;
- BMI (<25,  $\geq$  25 kg/m^2);
- Weight (<Median,  $\geq$ Median kg) ;
- Gender;
- Age (<65,  $\geq$ 65 years);
- Randomization strata as per registration center (With/Without statin at ACS onset);
- Diabetic status at baseline (Yes, No);
- Diabetic status at baseline relevant to insulin use (No diabetes, diabetes without insulin, diabetes with insulin);
- Diabetic status at baseline relevant to time from diagnosis of diabetes (No diabetes, diabetes for <Median years, diabetes for  $\geq$  Median years);
- Index ACS event (STEMI, NSTEMI, UA);
- Prior ischemic stroke(Yes, No);
- eGFR (<60,  $\geq$ 60 mL/min/1.73m^2) ;
- eGFR (<30,  $\geq$ 30 to <60,  $\geq$ 60 mL/min/1.73m^2); if sufficient number of patients in category  $\geq$  30 to <60, then combine category  $\geq$  30 to <60 and  $\geq$ 60; i.e. eGFR(<30,  $\geq$ 30);
- Baseline calculated LDL-C (<80,  $\geq$ 80 to <100,  $\geq$ 100 to <130,  $\geq$ 130 to <160,  $\geq$ 160 mg/dL) (ie, <2.07,  $\geq$ 2.07 to <2.59,  $\geq$ 2.59 to <3.37,  $\geq$ 3.37 to <4.14,  $\geq$ 4.14 mmol/L);
- Baseline calculated LDL-C (<100,  $\geq$ 100 to <130,  $\geq$ 130 to <160,  $\geq$ 160 mg/dL) (ie, <2.59,  $\geq$ 2.59 to <3.37,  $\geq$ 3.37 to <4.14,  $\geq$ 4.14 mmol/L);
- Baseline HDL-C (<40,  $\geq$ 40 mg/dL) (ie, <1.04,  $\geq$ 1.04 mmol/L);
- Baseline fasting TGs (<150,  $\geq$ 150 mg/dL) (ie, <1.7,  $\geq$ 1.7 mmol/L [mixed dyslipidemia]);
- Baseline Lp(a) (<30,  $\geq$ 30 to <50,  $\geq$ 50 mg/dL) (ie, <0.3,  $\geq$ 0.3 to <0.5,  $\geq$ 0.5 g/L);
- Baseline Lp(a) (<50,  $\geq$ 50 mg/dL) (ie, <0.5,  $\geq$ 0.5 g/L);

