#### **2.4.4.2 Analyses of secondary efficacy endpoints**

Method for controlling the overall type-I error rate when testing the key secondary efficacy endpoint is described in [Section 2.4.4.3](#).

For the key secondary efficacy endpoint (defined in [Section 2.1.3.2.1](#)) and the other secondary efficacy endpoints (described in [Section 2.1.3.2.2](#)), descriptive summaries and analyses will be performed in the mITT population.

For lipids parameters (calculated LDL-C, TC, HDL-C, fasting TGs, non-HDL-C, Apo B, Apo A-1, ApoB/Apo A-1 ratio, Lp(a), calculated LDL-C/HDL-C ratio, and fasting TGs/HDL-C ratio), all measurements, scheduled or unscheduled will be assigned to analysis windows defined in [Section 2.5.4.2, Table 4](#) in order to provide an assessment for time points. Laboratory assessments other than the ones provided by the central laboratory will be excluded. For TGs, measurements on not-fasting patients will be excluded. Analyses will be performed using standard international unit and conventional unit.

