### ***Binary endpoints***

Binary secondary endpoints defined in [Section 2.1.3.2.2](#) (i.e. The proportion of patients with calculated LDL-C <70 mg/dL (1.81 mmol/L) at Week 36, The proportion of patients with calculated LDL-C <50 mg/dL (3.37 mmol/L) at Week 36., and The proportion of patients achieving at least 50% reduction in calculated LDL-C at Week 36) will be analyzed using multiple imputation approach for handling of missing values(See above for details about multiple imputation). In the imputations, log-transform process planned above will not be done for the lipid parameter assuming normal distribution. The binary endpoint at time point of interest will be derived from observed and imputed lipid values at this time point. Multiple imputation will be followed by stratified logistic regression with treatment group as main effect and corresponding baseline value(s) as covariate, stratified by randomization strata (as per registration center, as defined in [Section 1.1](#)). Combined estimates of odds ratio versus placebo, 95% CI, and p-value will be obtained through the SAS MIANALYZE procedure.

In the data dependent case such logistic regression is not applicable (eg, the response rate is zero in 1 treatment arm and thus the maximum likelihood estimate may not exist), the last observation carried forward (LOCF) approach would be used for handling of missing values and a stratified exact conditional logistic regression would be performed to compare treatment effects. The LOCF imputation method for the endpoints at Week 36 will consist of using the last value obtained up to the Week 36 analysis window to impute the missing Week 36 value.

In case of computing issues with exact logistic regression, the baseline level(s) will be entered in the model as a categorical variable(s) using quartiles. In case the model would not converge with stratification variables, an unstratified exact logistic regression will be performed. Exact odds followed by logistic regression. In the data dependent case that the logistic regression method is not applicable (e.g., the response rate is zero in 1 treatment arm and thus the maximum likelihood estimate may not exist).

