#### **2.4.4.3 Multiplicity issues**

In order to handle the key secondary efficacy endpoint, the overall type-I error will be controlled by the use of a sequential inferential approach. Statistical significance of the primary efficacy endpoint at the 0.05 alpha level is required before drawing inferential conclusions about the key secondary efficacy endpoint (defined in [Section 2.1.3.2.1](#)). This fixed hierarchical approach will ensure a strong control of the overall type-I error rate at the 0.05 level.

No further adjustments will be made for other secondary endpoints other than key secondary endpoint for which p-values will be provided for exploratory purpose only (no claim).

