### ***Conversion to standard international unit***

Should not be rounded at the time of calculation for conversion to standard international unit.

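### The SAP prints 3.37 mmol/L beside its LDL-C <50 mg/dL responder threshold in two places; 50 mg/dL is 1.29 mmol/L, and 3.37 is the SAP's own figure for 130 mg/dL.

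*SAP*

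**What the plan says.** SAP section 2.1.3.2.2 adds three LDL-C responder endpoints at Week 36. Two are absolute thresholds, listed one after the other: "The proportion of patients with calculated LDL-C <70 mg/dL (1.81 mmol/L) at Week 36" and then "The proportion of patients with calculated LDL-C <50 mg/dL (3.37 mmol/L) at Week 36". The analysis text under Binary endpoints in SAP section 2.4.4.2 repeats the second pair: "calculated LDL-C <50 mg/dL (3.37 mmol/L) at Week 36". It derives the responder status from observed and imputed lipid values and does not name the unit to be used.

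For the lipid parameters, section 2.4.4.2 also says "Analyses will be performed using standard international unit and conventional unit". On conversion, section 2.5.1 says only "Should not be rounded at the time of calculation for conversion to standard international unit".

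Elsewhere the SAP gives 3.37 mmol/L a different meaning. The LDL-C subgroups in section 2.4.4.1 read "Baseline calculated LDL-C (<100, $\geq$ 100 to <130, $\geq$ 130 to <160, $\geq$ 160 mg/dL) (ie, <2.59, $\geq$ 2.59 to <3.37", so 3.37 mmol/L stands there for 130 mg/dL. The baseline LDL-C categories in section 2.1.1 do the same.

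The endpoint is not in the protocol's list of other secondary endpoints (section 9.1.2.2). SAP section 2.4.4.3 places it outside the testing hierarchy: for such endpoints "p-values will be provided for exploratory purpose only (no claim").

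**The concern.** A responder endpoint is defined by its cut-off, and here the definition carries two cut-offs that disagree. The error is in the endpoint list and again in the analysis section, so checking one against the other would not reveal it. The protocol does not list the endpoint, so it cannot settle the value either.

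The two absolute endpoints should be nested: anyone below 50 mg/dL is also below 70 mg/dL. With the printed SI values the order reverses, because everyone below 1.81 mmol/L is also below 3.37 mmol/L. The rate reported for <50 could then never be lower than the rate for <70, and would be higher as soon as one patient lay between the two SI cut-offs.

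The endpoint would also lose its meaning as a comparison. Both arms are managed to an LDL-C target below 100 mg/dL (2.59 mmol/L in the SAP), so every patient at target, in either arm, would count as a responder.

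**Working it through.** **Inputs, all from the SAP**
- Pair in question: 50 mg/dL with 3.37 mmol/L (sections 2.1.3.2.2 and 2.4.4.2).
- Adjacent endpoint: 70 mg/dL with 1.81 mmol/L (section 2.1.3.2.2).
- Other LDL-C pairs: 80, 100, 130, 160 and 190 mg/dL (section 2.1.1); 15 and 25 mg/dL (section 2.1.5.3).
- HDL-C pair: 40 mg/dL. Non-HDL-C pairs: 110 and 220 mg/dL (section 2.1.1).

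**Step 1: conversion factor.** From the adjacent endpoint, 70 / 1.81 = 38.67 mg/dL per mmol/L.

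**Step 2: does the factor reproduce the SAP's other pairs?** Computed value = mg/dL / 38.67.

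| mg/dL | printed mmol/L | computed | printed minus computed |
|---|---|---|---|
| 15 | 0.39 | 0.388 | +0.002 |
| 25 | 0.65 | 0.646 | +0.004 |
| 40 | 1.04 | 1.034 | +0.006 |
| 70 | 1.81 | 1.810 | 0.000 |
| 80 | 2.07 | 2.069 | +0.001 |
| 100 | 2.59 | 2.586 | +0.004 |
| 110 | 2.84 | 2.845 | -0.005 |
| 130 | 3.37 | 3.362 | +0.008 |
| 160 | 4.14 | 4.138 | +0.002 |
| 190 | 4.91 | 4.913 | -0.003 |
| 220 | 5.69 | 5.689 | +0.001 |
| **50** | **3.37** | **1.293** | **+2.077** |

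Eleven of the 12 pairs agree within 0.01 mmol/L. Only the 50 mg/dL pair fails.

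**Step 3: what the printed value means.** 3.37 x 38.67 = 130.3 mg/dL. Against the intended threshold, 130.3 / 50 = 2.61 and 130.3 - 50 = 80.3 mg/dL.

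**Step 4: does the choice of factor matter?** The 11 consistent pairs imply factors from 38.46 to 38.73. Over that range:
- 50 mg/dL is 50 / 38.73 = 1.29 to 50 / 38.46 = 1.30 mmol/L.
- 3.37 mmol/L is 3.37 x 38.46 = 129.6 to 3.37 x 38.73 = 130.5 mg/dL.

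The failing pair would need a factor of 50 / 3.37 = 14.84. A triglyceride factor does not explain it: the SAP's 400 mg/dL with 4.52 mmol/L gives 88.5, and 50 / 88.5 = 0.56.

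**Step 5: order of the two endpoints.** In mg/dL, 50 < 70. In the printed SI values, 3.37 > 1.81. With the corrected value, 1.29 < 1.81 and the order is restored.

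No responder rates are computed, because neither document gives a distribution of LDL-C at Week 36.

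**The case against.** The arithmetic is not open to dispute, so the case on the other side concerns the consequence.

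- **The intended threshold is clear.** Section 2.5.1 defines calculated LDL-C in mg/dL, with the divisor of 5 that belongs to that unit. The paired LDL-C thresholds put mg/dL first and mmol/L in parentheses, and the titration summary in section 2.4.3.1 uses mg/dL alone.
- **A proportion has no unit.** A patient below 50 mg/dL is the same responder in either presentation. Where the SAP spells out two-unit reporting, under Descriptive summaries, it concerns raw values and changes from baseline.
- **The error would probably be noticed.** A wrong SI run would disagree with the mg/dL run of the same endpoint, and could show more patients below 50 than below 70 mg/dL.
- **Little depends on it.** The endpoint is exploratory, and the other LDL-C endpoints are unaffected.

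Most of this stands. It makes a misread cut-off unlikely and limits the damage if one occurs. It does not make the definition right. No sentence says that the mg/dL figure overrides a printed SI threshold, and the conversion rule in section 2.5.1 concerns rounding when values are converted. The sentence calling for both unit systems covers the lipid parameters without excepting the binary endpoints. Even with correct programming, a table title copied from the SAP would state a false threshold.

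**Conclusion.** The concern holds. The printed SI equivalent is wrong in both places: 3.37 mmol/L where 50 mg/dL is 1.29 mmol/L, too high by 2.08 mmol/L (about 80 mg/dL), a factor of 2.6. The result rests only on the SAP's own conversion pairs and does not change across the factors they imply.

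The effect on results is conditional. It arises only if a programmer derives the responder flag in mmol/L from the printed number. If 50 mg/dL is used directly, or converted without rounding, the responders are correct. The primary and key secondary IVUS analyses, the sample size, the <70 mg/dL and 50%-reduction endpoints and the continuous LDL-C analyses are not affected. This should be corrected, but it does not threaten the trial's main conclusions.

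**What to change.** Replace 3.37 mmol/L by 1.29 mmol/L beside the <50 mg/dL threshold in SAP section 2.1.3.2.2 and in the Binary endpoints text of section 2.4.4.2.

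Optionally, add one sentence to the Binary endpoints text: responder status is derived from the mg/dL threshold, and the same flag serves both unit presentations. That removes the route to the error and also prevents small disagreements between unit systems caused by rounded SI cut-offs.

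The cost is two number corrections and, if wanted, one sentence. No new data or analysis is needed.
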